8.6.8 Grading of Adverse Event severity

Severity is a clinical determination of the intensity of an AE. The severity for an AE should be graded using the National Cancer Institute's Common Terminology Criteria for Adverse Events (CTCAE, version 4.03).

In case of AEs that are not described in the CTCAE v 4.03, the investigator will use the terminology MILD, MODERATE, SEVERE or LIFE-THREATENING to describe the maximum severity of the adverse event as follows:

- MILD (grade 1) The subject is aware of the event or symptom but the event or symptom is easily tolerated (i.e. no reduction in daily activities of the subject)
- MODERATE (grade 2) The subject experiences sufficient discomfort to interfere with or reduces his or her usual level of activity.

- SEVERE (grade 3) Significant impairment of functioning: the subject is unable to carry out usual activities and/or the subject's life is at risk from the event.
- LIFE-THREATENING (grade 4) The subject experiences immediate life-threatening consequences which requires urgent intervention.

This information on AE grading will be entered in the adverse event CRF.

It is to be noted the distinction between severity (intensity) and seriousness of adverse events. A severe adverse event is not necessarily a serious adverse event.

8.6.9 Adverse Event causality assessment

For each serious and non-serious adverse events, the investigator is required to assess if there is a causal relationship between the adverse event and the study drugs, i.e. to determine whether **there is at least a reasonable possibility** that one of both study drugs caused or contributed to the adverse event. This means that there are facts and arguments to suggest a causal relationship.

To help investigators with the decision binary tree in the evaluation of causality, the CIOMS VI group recommends that investigators be asked to consider the following before reaching a decision:

- Medical history
- Lack of efficacy/worsening of existing condition
- Study medications
- Other medications (concomitant or previous)
- Withdrawal of study medication, especially following trial discontinuation / end of study medication
- Erroneous treatment with study medication (or concomitant)
- Protocol related procedure

Using this information, the investigator will classify each adverse event as:

- **Not related:** There is no reasonable possibility of causal relationship between an AE and study drug
- **Related:** There is at least a reasonable possibility of a causal relationship between an AE and a study drug. This means that there are **facts** (evidence) or arguments to suggest a causal relationship.

The decision to suspend, and resume treatment or to permanently interrupt treatment due to an adverse event will be left to the clinician in charge.

8.6.10 Exposure in utero

All pregnant women are excluded from the trial. This is specifically due to the teratogenic potential of miltefosine (demonstrated in rats). The manufacturer and Sponsor recommend that effective contraception should be used during and up to 5 months after treatment of miltefosine.

If any trial subject becomes or is found to be pregnant within the initial 6 months of her participation in this trial the investigator must submit the event on the Pregnancy Report form. This must be done irrespective of whether an adverse event has occurred. The information submitted should include the anticipated date of delivery.

The investigator will follow the subject until completion of the pregnancy or until pregnancy termination (i.e., induced / spontaneous abortion). The investigator will provide pregnancy outcome information in the Pregnancy Outcome report form.

A pregnancy is not an SAE.

In the case of a live birth, a pediatrician should assess the infant at the time of birth and submit a Child report. An SAE should be declared in the case of unfavourable pregnancy outcome (abortion, still birth) or congenital abnormality. In case of *in utero* exposure, the parents will be proposed a follow-up of the new-born up to the age of 2 years old.

8.6.11 Adverse event follow up

All adverse events should be followed until they are resolved or the investigator assesses them as chronic or stable or the subject participation in the trial ends (i.e., until a final report is completed for that subject).

In addition, all serious adverse events and those non-serious events assessed by the investigator as possibly related to the investigational drug must continue to be followed even after the subject participation in the trial is over. Such events should be followed until they resolve or until the investigator assesses them as "chronic" or "stable." Resolution of such events is to be documented on the CRF and SAE form.

9 Withdrawal criteria

A subject should be withdrawn from the study treatment if, in the opinion of the investigator, it is medically necessary, or if it is the wish of the subject.

If a subject does not return for a scheduled visit, every effort should be made to contact the subject. In any circumstance, every effort should be made to document subject outcome, if possible.

If the subject withdraws consent, no further evaluations should be performed and no attempts should be made to collect additional data, with the exception of safety data, which should be collected if possible and in accordance with patient consent. If a subject withdraws from the study, the reason must be noted on the CRF.

If a subject is withdrawn from the study because of a treatment limiting adverse event, thorough efforts should be made to clearly document the outcome of AE.

9.1 Rules in case of treatment suspension or interruption

In the event that treatment is interrupted (e.g. due to an adverse event), the decision to resume treatment will be taken by the site Principal Investigator. If miltefosine treatment is interrupted for more than 3 days and requires additional PKDL treatment (other than that described in the protocol) they will be considered a treatment failure for the purposes of the ITT analysis and excluded from the per protocol analysis. If interruption was for 3 or less days,

treatment will start again till the complete dose is administered.

Note that for the Ambisome[®] treatments, delay for >1 week of the administration of a dose which requires additional PKDL treatment (other than that described in the protocol), they will be considered a treatment failure for purposes of ITT analysis and excluded from the per protocol analysis. If interruption was for 6 or less days, treatment may start again at discretion of the investigator, until the complete dose is administered.

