10.3 Definition of study populations included in the analysis

For the primary analysis, an intention to treat (mITT) and per protocol (PP) analysis will be performed.

- Modified ITT population (mITT): all randomized patients receiving at least one dose of treatment. In case of error of treatment allocation, the actual treatment received will be used in the analysis. Modified ITT set of patients will be used in the primary and secondary efficacy analysis and in safety analysis.
- Per protocol population (PP): subset of patients belonging to the modified ITT and who did not have major protocol violations. Major protocol violations are any violation that may bias the result of the study, which will be defined a priori in the statistical analysis plan.

To take account of missing data, each of the above analysis sets (mITT and PP), the efficacy endpoints will be calculated in two ways: worst case scenario (missing outcome is defined as failure) and complete case analysis (missing outcome is excluded from the analysis, population is defined as set of completers).

• Set of completers: subset of patients belonging to the mITT or PP, who attended the 12 months follow-up visit. This set will be used in a sensitivity analysis of the primary

efficacy analysis.

A sensitivity analysis will also be performed for the secondary efficacy endpoints with the subset of patients who attended the 12 and 24-months follow-up visits.

Missing outcome data on the efficacy endpoints could arise if a patient withdraws consent, is lost to follow-up, or has an exam omitted by investigator oversight in patients who are not confirmed as cured.

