10.6 Efficacy Analysis

Efficacy of the treatment will be assessed at 12 and at 24-month follow-up visit. The efficacy estimate will be reported as proportion of cured with its 95% confidence interval.

The data will be analysed as proportion, according to either mITT or PP populations.

Definitions

- **Cure**: Complete resolution of papular and nodular lesions (flattening of 100% of lesions) and significant improvement (> 80% re-pigmentation, as per scoring system, section 8.3.1) of macular lesions at 12 or at 24 months follow-up visits.
- Treatment Failure:

A patient will be considered a treatment failure:

- If rescue treatment is indicated by the investigator due to:
 - Non-response to treatment or worsening of PKDL lesions anytime during the treatment phase of the study
 - Occurrence of adverse events that leads to treatment discontinuation and require rescue treatment
 - Relapse: patient presented clinical response/improvement of lesions, but in subsequent follow-up visits the investigator observes appearance of new lesions and/or worsening of PKDL lesions, and indicates rescue treatment at any-time during follow-up period, including 24 months visit.

Or

• Patient did not fulfil the criteria for cure at the 12 or 24-months follow-up: presenting persistence of papular or nodular lesions and/or not significant improvement (< 80% re-pigmentation, as per section 8.3.1) of macular lesions.

• Lost to Follow Up: Patient did not turn up for 24 month follow up assessment and could not be contacted by health educators.

In addition, the overall clinical presentation of the patient will be assessed by the Investigator using the following categories ³⁴:

- Category 1: All lesions have improved and the majority of lesions have resolved. Any remaining lesions are only faintly visible as re-pigmentation is almost complete.
- Category 2: The majority of lesions show significant improvement, some lesions have resolved
- Category 3: No new lesions, but the majority of lesions show no or slight improvement.
- Category 4: New lesions have appeared and there is no or little improvement of other lesions

The proportion of PKDL patients in category 1, 2, 3 and 4 with its 95% confidence interval will be summarized per study arm, at 12 and at 24 months follow-up visits.

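### Section 9.1 makes per-protocol exclusion after a long interruption conditional on needing further PKDL treatment, so membership of that set depends on outcome

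*Protocol*

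**What the plan says.** Protocol section 9.1 has two parallel paragraphs. For miltefosine the trigger is "If miltefosine treatment is interrupted for more than 3 days and requires additional PKDL treatment"; for Ambisome it is a "delay for >1 week of the administration of a dose which requires additional PKDL treatment". In both, the consequence is that "they will be considered a treatment failure for the purposes of the ITT analysis and excluded from the per protocol analysis". For a patient with an interruption of the same length and no additional treatment, 9.1 states no PP exclusion.

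Other sections bear on this:

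- **7.8** makes any patient who receives rescue treatment a treatment failure.
- **10.6** lists as a failure: "Occurrence of adverse events that leads to treatment discontinuation and require rescue treatment". It adds: "The data will be analysed as proportion, according to either mITT or PP populations".
- **7.2** leaves rescue to the investigator's discretion when treatment is interrupted for more than 72 hours because of an adverse event. Section 7.6 confirms that the study is open label.
- **10.3** says: "For the primary analysis, an intention to treat (mITT) and per protocol (PP) analysis will be performed". It then assigns the sets: "Modified ITT set of patients will be used in the primary and secondary efficacy analysis and in safety analysis". PP is the "subset of patients belonging to the modified ITT and who did not have major protocol violations", with the list of major violations left to the SAP.

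**The concern.** A per-protocol set is meant to hold patients who received the treatment as planned, and membership should be settled by exposure and conduct. Section 9.1 adds a second condition, the need for other PKDL treatment, which is part of the outcome. Two patients with identical incomplete courses can be handled differently under 9.1 because one failed and the other did not. Where an adverse event has interrupted treatment for more than 72 hours, the deciding step is a discretionary choice by an investigator who knows the allocation.

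Compared with keeping these patients in PP as failures, the rule can only raise the PP cure rate. That estimate is reported beside mITT in the primary analysis, so a reader may take it as the efficacy of the regimen when properly given, although failures have been removed because they failed.

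**Working it through.** **Inputs.** From section 10.1: anticipated cure 85%, target precision 10 points with a 95% CI, 50 patients per arm raised to 63 for 10% loss and 15% treatment discontinuation. The protocol gives no rate of interruption followed by additional treatment, so the number affected, k, is an assumption and is varied.

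**The plan's own figure.** Half-width at n = 50: 1.96 × √(0.85 × 0.15 / 50) = 0.099, or 9.9 points. Inflation: 50 × 1.25 = 62.5, taken as 63. Both stated figures reproduce. They serve here only as a scale for the effect.

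**Step 1: is the second condition an outcome?** Section 9.1 calls these patients failures for the ITT analysis. Sections 7.8 and 10.6 make rescue a failure as well. I read additional PKDL treatment in 9.1 as including rescue, but the conclusion does not rest on that reading, because 9.1 applies the failure label itself. Everyone removed by this rule is therefore a failure.

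**Step 2: 9.1 against keeping the same patients as failures.** Let C be the number cured among the 63 − k patients kept, with C = 0.85 × (63 − k) rounded, and no other exclusions or losses.

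- PP under 9.1 = C / (63 − k)
- Same patients kept as failures = C / 63
- Gap = [C / (63 − k)] × (k / 63), about 0.85 times the share affected

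| Share affected | k | PP under 9.1 | Kept as failures | Gap |
|---|---|---|---|---|
| 5% | 3 | 51/60 = 85.0% | 51/63 = 81.0% | 4.0 points |
| 10% | 6 | 48/57 = 84.2% | 48/63 = 76.2% | 8.0 points |
| 15% | 9 | 46/54 = 85.2% | 46/63 = 73.0% | 12.2 points |

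The 15% row treats every discontinuation anticipated in 10.1 as needing other treatment, so it is an upper bound on the planning figures. Its exact 95% intervals are 72.9 to 93.4% and 60.3 to 83.4%. With no other exclusions, the right-hand estimate keeps all 63 patients and equals the mITT estimate. The gap is thus the mITT-to-PP difference that the rule creates.

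**Step 3: 9.1 against a PP set based on exposure alone.** Assume 9 interrupted patients in an arm of 63, and 46 cured among the other 54. Excluding all 9 on exposure gives 46/54 = 85.2%. The splits below are illustrative; the protocol gives none.

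| Of the 9 interrupted | PP under 9.1 | Difference from 85.2% |
|---|---|---|
| 3 need other treatment, 6 do not and all are cured | 52/60 = 86.7% | +1.5 |
| 5 need it, 4 do not and all are cured | 50/58 = 86.2% | +1.0 |
| 5 need it, 4 do not and 3 are cured | 49/58 = 84.5% | −0.7 |
| 5 need it, 4 do not and 2 are cured | 48/58 = 82.8% | −2.4 |

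The sign depends on whether the interrupted patients who stay in do better or worse than the 85.2% in the rest. These comparisons also assume that the SAP does not exclude those patients on other grounds.

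**The case against.** The strongest reply is that 9.1 gives an explicit rule, and that leaving incompletely treated patients out of PP is ordinary practice. Several parts of this stand.

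- A reader might infer that 9.1 contradicts 10.6. It does not strictly do so: 10.6 defines outcomes, 9.1 and 10.3 define membership, and a patient can meet the failure definition and lie outside PP. Naming mITT and PP as the sets analysed does not require these patients to remain in PP.
- A reader might call PP co-primary. The protocol does not use that term. Section 10.3 names PP for the primary analysis but assigns mITT to primary efficacy. The trial is non-comparative and reports proportions with confidence intervals, so no error rate is at stake, and the failures stay visible in mITT.
- A reader might conclude that partly treated cures remain in PP. Section 9.1 alone would leave them there, but the SAP may exclude them as major violations. Section 7.2 already defines full compliance.
- The group interrupted without further treatment may be small, because 7.2 and 9.2 direct attention to further treatment once a course is not completed.
- Different time limits for the two drugs, with the miltefosine limit applying only to the combination arm, might suggest a biased comparison. No between-arm comparison is planned, and one drug is taken daily while the other is given on five separate days, so this carries little weight.

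What the reply does not answer is that ordinary PP exclusion rests on exposure, whereas 9.1 rests on exposure together with failure. A SAP list of further violations could reduce the asymmetry, but it would not make this stated rule independent of outcome.

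**Conclusion.** The point holds as a defect in how section 9.1 defines PP membership. The rule selects on outcome and, after adverse-event interruptions over 72 hours, on an open-label discretionary decision. Its effect is confined to PP.

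Relative to keeping the patients as failures, PP is higher by about 4, 8 or 12 points when 5%, 10% or 15% of an arm of 63 is affected, assuming 85% cure in those kept. At the upper bound this exceeds the planned 10-point precision. The true share is unknown.

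It would be tempting to read those gaps as inflation over a properly built PP set. The arithmetic does not show that: against an exposure-only PP the illustrations differ by about 1 to 2 points, in either direction. The reason to change the rule is that membership should not depend on outcome, and the change is cheap.

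**What to change.** In both paragraphs of section 9.1, remove the need for additional PKDL treatment as a condition for PP exclusion, and align the text with 10.3. PP exclusion would then rest on exposure alone, for example the existing 7.2 threshold of 90% of the prescribed dose, applied in both arms whatever happens afterwards. A total-dose threshold does not capture a delayed but complete course. If delay is also meant to exclude, state it on the length of delay alone. Patients needing additional treatment remain failures in mITT; replace ITT by mITT in 9.1, because 10.3 defines only the modified set.

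Alternatively, delete the PP exclusion from 9.1 and keep these patients in PP as failures.

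The cost is wording in 9.1 and matching text in the SAP; dosing and compliance data are already collected. Under the first option a few partly treated cures leave PP. Under the second the PP cure rate is less favourable and moves close to mITT. Neither option alters the clinical rules on interruption or rescue, and no change to those is proposed.

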9.2 Rules for permanently interrupting study treatment

If a subject is withdrawn from the study before the full course of the treatment is completed, the physician must make all necessary arrangements to ensure that the subject receives the appropriate treatment for the relevant medical condition (e.g. with drug/s currently recommended by the national policy).

9.3 Subject withdrawal from the study and subject replacement

Subjects withdrawn from the study will not be replaced.

10 Data Analysis and Statistical Methods

10.1 Sample size determination

We estimated that a minimum sample size of 50 subjects per treatment arm would provide a precision estimate of 10% with 95% CI, based on an anticipated cure rate at 12 months in 85% of patients. Accounting for 10% subjects lost during follow up and 15% subjects with treatment discontinuation, 13 more subjects were added per arm resulting an increase of the sample size to 63 for each regimen. The overall sample size for the two regimens is 126 subjects.

The anticipated cure rate was selected based on the criteria set on the cure rates previously reported with the use of Miltefosine or Ambisome[®] alone.

A computer generated, randomization code will be used for patient treatment allocation to one of the two treatment arms indicated.

Eligible patients who fulfil all the inclusion criteria and have none of the exclusion criteria, and from whom informed consent has been obtained, will be randomized to one of the treatment regimens.

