In a recent field experience by MSF on routine patient management in Bangladesh (Fulbaria), 1400 patients were treated with Ambisome[®] 6 x 5 mg/kg given over 2 weeks. Results were satisfactory, with 86.5% of patients presenting total disappearance of all nodular and papular lesions and complete or very significant re-pigmentation of macular lesions after one year of follow-up. Among the 13.5% of cases who did not have significant re-pigmentation of macular lesions at 12 months, improvement was observed in subsequent visits, and only 2% of the patients required a second course of treatment. This experience was based on clinical assessment in the field, and not done systematically by standardized procedures. In order to better characterize the Ambisome treatment for PKDL patients in Bangladesh, MSF conducted a clinical trial where patients were again treated with Ambisome[®] 30mg/kg (n=110). In this

Protocol Version/Date: V3.0, 25 Feb 2020

trial, treatment outcome was standardised, including photographs and evaluated independently by clinicians. A total of 88 patients completed 12 months follow up, out of which 80% responded satisfactorily to treatment (67% patients had complete resolution of lesions and 13% had substantial improvement (>75%) of lesions). In this study however, severe side-effects were noted as rhabdomyolysis was reported in 6 patients, 3 of which had severe hypokalemia that was ascribed to Ambisome[®] therapy. In an on-going second study, patients are treated with 5 x 3 mg/kg (2 injections per week) with potassium and magnesium supplementation and intensive monitoring. Preliminary reports do not suggest severe hypokalemia occurring during this regimen, and patients are responding to treatment satisfactorily.

In addition, expert opinion in Bangladesh is that patients with severe PKDL in Bangladesh had to be treated with high total doses of Ambisome (up to 60mg/Kg total dose) and careful monitoring of treatment help to prevent severe hypokalemia or rhabdomyolisis ([name], personal communication). Perhaps severe PKDL leads to significant destruction of the skin and this, in addition to higher dose of AmBisome, facilitate better penetration of the drug to the skin. This emphasizes the need of skin PK analysis of anti-PKDL drugs and to correlate it with response to treatment.

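### The loss allowance in Section 10.1 was multiplied in rather than divided out, so 63 per arm leaves 47–48 rather than the stated 50, and the 85% is not tied to an analysis set or missing-data rule

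*Protocol*

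**What the plan says.** Protocol Section 10.1, with matching text in the Statistics row of the synopsis, sizes the trial on precision alone: "We estimated that a minimum sample size of 50 subjects per treatment arm would provide a precision estimate of 10% with 95% CI". The cure rate assumed for this is 85% at 12 months. The allowance is 10% for loss to follow-up and 15% for patients who stop treatment, and its stated effect is that "13 more subjects were added per arm resulting an increase of the sample size to 63 for each regimen". Both arms together therefore make 126 patients. Section 9.3 rules out replacing withdrawn patients.

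Section 10.3 defines the modified ITT set (everyone randomised who received at least one dose), used for the primary efficacy analysis, and a per-protocol set without major violations. Each is analysed in two ways: a "worst case scenario (missing outcome is defined as failure", and a complete-case analysis that leaves missing outcomes out. The completers set is assigned to a sensitivity analysis.

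Under Section 10.6, a discontinuation for an adverse event is a treatment failure when rescue treatment is also required. Section 9.1 likewise ties failure and per-protocol exclusion after an interruption to a need for additional PKDL treatment.

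**The concern.** Two things do not fit together.

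- **The inflation.** An allowance for losses should return the required number after the losses have occurred. Adding 25% of 50 does not, because the 25% is then lost from the larger number. The section calls 50 a minimum, and its own assumptions lead to fewer.
- **The 85%.** Adding patients to offset losses makes sense when lost patients leave the denominator. In the mITT worst-case analysis they stay in it as failures. Section 10.1 does not say which of these situations the 85% and the 10 points describe.

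The trial is non-comparative and descriptive, so no test or success threshold depends on this. But precision is the only sizing criterion, and a reader will judge the final confidence intervals against it.

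**Working it through.** **Inputs.** From Section 10.1: cure rate p = 0.85, target half-width d = 0.10, 95% confidence (z = 1.96), 50 per arm, 10% lost, 15% discontinued, 63 per arm. From Section 9.3: no replacement. From Section 10.3: analysis sets and missing-data rules. The protocol names no interval method. The normal (Wald) approximation is used here because it reproduces the protocol's figure.

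**1. The stated minimum.** n = z² p(1 − p) / d² = 1.96² × 0.85 × 0.15 / 0.10² = 48.98, so 49. The stated 50 agrees. Its half-width is 1.96 × √(0.1275 / 50) = 9.9 points.

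**2. The stated inflation.**
- 50 × 1.25 = 62.5, so 63. This matches.
- 50 / 0.75 = 66.7, so 67.
- 50 / (0.90 × 0.85) = 65.4, so 66, if the losses act in sequence.

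Of these, only the multiplication gives 63.

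**3. What 63 leaves.**
- Losses added: 63 × 0.75 = 47.25, about 47.
- Losses in sequence: 63 × 0.90 × 0.85 = 48.2, about 48.

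**4. Half-width at 85%, by analysis: 1.96 × √(0.1275 / n).**

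| Analysis | n per arm | Half-width (points) |
|---|---|---|
| Stated minimum | 50 | 9.9 |
| Both groups excluded, losses in sequence | 48 | 10.1 |
| Both groups excluded, losses added | 47 | 10.2 |
| mITT complete-case (63 × 0.90 = 56.7) | 57 | 9.3 |
| mITT, all 63, if 85% is the rate in all of them | 63 | 8.8 |

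The rows for 47 and 48 fit per-protocol complete-case only, and only if every discontinuation is a per-protocol exclusion.

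**5. Worst-case mITT, if 85% is the rate among patients with an outcome.** With the planned 10% lost and counted as failures:
- expected rate = 0.90 × 0.85 = 76.5%
- half-width at 63 = 1.96 × √(0.765 × 0.235 / 63) = 10.5 points
- n for 10 points = 1.96² × 0.765 × 0.235 / 0.10² ≈ 69.1, so 70 per arm

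Correcting the inflation to 67 would therefore not by itself restore 10 points for this analysis.

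**6. The converse.** If 85% is meant as the worst-case mITT rate, then with 10% lost the others must be cured at 0.85 / 0.90 = 94.4%.

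**The case against.** The strongest reply is that the slip hardly matters. The unrounded requirement is 49, so the shortfall is one or two patients, and 10.1–10.2 points still rounds to 10. In the mITT set used for the primary analysis, precision at 85% is better than promised. This stands: the error is real but its effect on precision is small, and it would not justify enlarging the trial.

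A second reply is that Section 10.1 speaks only of 85% of patients and never says evaluable patients. This also stands, and it limits the second part of the point to a failure to reconcile the figures. It does not make 85% wrong.

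Three stronger readings are tempting, and the protocol does not support them.

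- A reader might infer that the worst-case mITT rate cannot be 85%. That would follow only if all 25% counted as failures, which caps the rate at 75%. If only the 10% lost are failures, the cap is 90%, and 85% is possible, though it needs 94.4% cure in the rest.
- A reader might infer an expected rate as low as 0.75 × 0.85 = 63.75%. This makes every discontinuation a failure. Section 10.6 does so for an adverse-event discontinuation only where rescue is required, and Section 10.3 does not list discontinuation among the sources of missing outcomes. Discontinuations that end in rescue may already sit within the anticipated 15% not cured, so subtracting them again risks counting them twice.
- A reader might cite the 30 mg/kg trial in Section 1.4 as evidence that 85% is too high. That trial used a different total dose and a different response threshold (over 75% improvement, against over 80% re-pigmentation here). Section 10.1 does not name it as the source of the 85%.

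**Conclusion.** The inflation error holds. The figure 63 arises from 50 × 1.25, and under the protocol's own losses with no replacement it leaves 47–48 per arm, not the stated minimum of 50. The size is small: 10.1–10.2 points instead of 9.9, and only in an analysis that drops both the lost and the discontinued. The mITT complete-case analysis gives 9.3 points, and mITT with all 63 at 85% gives 8.8.

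The second part holds as a gap in reconciliation. The 85% and the 10 points are not tied to an analysis set or missing-data rule. If 85% is the rate among patients with an outcome, the worst-case mITT analysis should expect 76.5% with a half-width of 10.5 points at 63.

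These results rest on Wald intervals, on the stated loss rates, and, for the 76.5%, on an assumption about what the 85% means that the protocol neither states nor excludes.

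**What to change.** Keep 126 patients. In Section 10.1 and the synopsis:

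1. State that 63 per arm yields about 47–48 patients after the stated losses, with a 95% half-width of about 10.2 points at 85%.
2. Say which analysis set and which missing-data rule the 85% and the 10-point precision refer to.
3. If 85% is a rate among patients with an outcome, give the worst-case mITT figures beside it: 76.5%, ±10.5 points at 63 per arm.

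The cost is a text change in two places and a slightly less favourable stated precision. No patients, visits or analyses are added.
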